9. DATA COLLECTION, MONITORING, AND AE REPORTING

9.1 Confidentiality

Information about study participants will be kept confidential to the best of the study site's ability.

In the event that a participant revokes authorization to collect or use personal health information (PHI), the sponsor retains the ability to use all information collected prior to the revocation of participant authorization. For participants that have revoked authorization to collect or use PHI, attempts should be made to obtain permission to collect at least vital status (i.e., that the participant is alive) at the end of their scheduled study period.

9.2 Source Documents

Source data is all information, original records or clinical findings, observations, or other activities in a clinical trial necessary for the reconstruction and evaluation of the trial. Source data are contained in original source documents. Examples of these original documents and data records include (as applicable): hospital records, clinical and office charts, laboratory notes, memoranda, participant's diaries or evaluation checklists, pharmacy dispensing records, recorded data from automated instruments, copies or transcriptions certified after verification as being accurate and complete, microfiches, photographic negatives, microfilm or magnetic media, x-rays, participant files, pharmacy records, laboratory records, medical records (including electronic records) relative to the clinical trial.

9.3 Data Collection

Data will be collected using Electronic Data Capture (EDC). Participants will be identified by PID#. Initial data collection may utilize a paper form of the EDC. Any such records will be maintained as source data.

9.4 Record Retention

It is the Investigator's responsibility to retain study essential documents as per country regulations: in the US for at least 2 years after the last approval of a marketing application in their country and until there are no pending or contemplated marketing applications in their country or at least 2 years have elapsed since the formal discontinuation of clinical development of the investigational product. The sponsor will inform the investigator/institution as to when these documents are no longer needed to be retained.

9.5 Safety and Quality Monitoring and Record Availability

Monitoring

Monitoring of the clinical trial will be performed by experienced monitors, who will report to the Sponsor as outlined in the Monitoring Plan.

Record availability and auditing

The investigator will make study documents (e.g., ICFs, drug accountability forms) and pertinent hospital or clinic records readily available for inspection by the local IRB, the site monitors, regulatory agencies, GeneOne Life Science, Inc. or its designee for confirmation of the study data.

Participation as an investigator in this study implies acceptance of potential inspection by regulatory authorities and applicable compliance and quality assurance offices.

9.6 Adverse event (AE) Reporting

AEs will be recorded and forwarded to regulatory agencies as required.

9.6.1 Study Reporting Period of Adverse Events

All AEs will be recorded throughout the study and the 28 day follow-up period.

9.6.2 Study Reporting Period for Serious Adverse Events

SAE's will be recorded throughout the study and the 28-day follow-up period.

Expedited reporting of SAEs will be determined by GeneOne Life Science using reference safety information specified in the Investigator's Brochure. An event may qualify for expedited reporting to regulatory authorities if it is an SAE, SUSAR in line with relevant regulatory requirements.

At any time after completion of the SAE reporting period, if an Investigator becomes aware of an SAE that is suspected by the Investigator to be related to the study drug, the event will be reported to the Sponsor.

SAE REPORTING	Catalyst Pharmacovigilance	[contact]
MEDICAL MONITOR:	[name] PhD MBA	MAILING ADDRESS:
[contact]p; [contact] c	GeneOne Life Science, Inc.
MEDICAL LIAISON:	[name] DPT	[name]
[contact]	[name]
EMAIL:	[contact]	[name]
24 hr Answering Service	[contact]	
GeneOne [contact]	
GeneOne Safety Email	[contact]	

SAE TELEPHONE AND CONTACT INFORMATION:

The report should contain as much clinical safety information as possible, but at minimum, the initial report must include the following information:

- Participant number and Study name
- Date of Onset and Date of Resolution (if applicable)
- Detailed description of event
- Investigational product (if known)
- Causal relationship of event to investigational product
- Reporter name and contact information

Follow-up reports will be sent as soon as more information becomes available. Events for which the study participant seeks medical care, the study site will attempt to obtain relevant medical records to include as source documents. These include but are not limited to discharge summary, results of relevant laboratory tests, and reports of relevant radiographic studies. In the case of death, the investigator will attempt to procure relevant reports (such as autopsy reports, medical examiner report, discharge summary).

Each SAE must be followed by the investigator until resolution, stabilization, or return to baseline, even if this extends beyond the end of the study, with follow-up report filed to provide a summary of the event through resolution.

The electronic data capture (EDC) system is integrated to the safety database (Veeva) vault and all SAE information will be collected electronically. A paper SAE form will be available as a back-up. Copies (or electronic copy) will be provided to GeneOne Life Science or its representative, who will be responsible for reporting to regulatory authorities as indicated, and copy will be forwarded to the study sites IRB/REC.

9.6.3 Notification of Serious Adverse Events

In accordance with local regulations, the Sponsor shall notify the appropriate regulatory authorities, and all participating investigators in a written safety report of any adverse experience associated with the use of the product that is both serious and unexpected (e.g., FDA Form 3500A in the US). SUSARs reports shall be made as soon as possible and in no event later than 15 calendar days after the Sponsor's initial receipt of the information. Written notification may be submitted on the form described above or equivalent or in a narrative format and shall bear prominent identification of its contents. Each written notification to regulatory agencies shall be transmitted to the division that has responsibility for review. In each written safety report, the Sponsor shall identify all safety reports previously filed concerning a similar adverse experience, and shall analyze the significance of the adverse experience in light of the previous, similar reports. The Sponsor shall also notify the relevant regulatory authorities by telephone, facsimile, or email transmission of all deaths and any unexpected fatal or life-threatening experience, regardless of causality, as soon as possible but in no event later than 7 calendar days after the Sponsor's initial receipt of the information. Each telephone call or facsimile transmission to regulatory agencies shall be transmitted to the division that has responsibility for review.

Follow up information to a safety report shall be submitted as soon as the relevant information is available. If the results of a Sponsor's event investigation show that an adverse drug experience not initially determined to be reportable is, in fact, reportable, the Sponsor shall report such experience in a written safety report as soon as possible, but in no event later than 15 calendar days after the determination is made. Results of investigations of other safety information shall be submitted, as appropriate, in an information amendment or annual report. In the event of death, if an autopsy is performed, a copy of the report, redacted for PHI but labeled with the PID#, should be sent to GeneOne Life Science, Inc.

9.7 Study Termination

GeneOne Life Science reserves the right to terminate the study for safety or administrative reasons, including lack of enrollment, at any time. Investigational product must be returned to GeneOne, unless instructed otherwise. Document retention will follow local regulation.

10. PUBLICATION OF RESEARCH FINDINGS

Publication of the results of this trial will be allowed. Any proposed presentation, abstract and/or manuscript must be made available to GeneOne at least 60 days prior to submission. GeneOne shall have fifteen (15) days for review. If GeneOne considers that material would reveal protectable intellectual property, GeneOne may request a delay in submission for a maximum of three (3) months from the date of receipt in order for patent application(s) to be filed with the United States Patent and Trademark Office and/or foreign patent office(s).

11. LIST OF ABBREVIATIONS

AE	Adverse event
Alk Phos	Alkaline phosphatase
ALT	Alanine transaminase
AST	Aspartate transaminase
BUN	Blood urea nitrogen
CBC	Complete blood count
CI	Confidence interval
CMP	Complete Metabolic Profile
CPAP	Continuous positive airway pressure
CPK	Creatinine phosphokinase
COPD	Chronic obstructive pulmonary disease
CRP	C-reactive protein
CTCAE	National Cancer Institute Common terminology criteria for adverse events
CXR	Chest X-ray (chest radiograph)
CRS	Cytokine release syndrome
DSMB	Data and Safety Monitoring Board
ECG	Electrocardiogram (synonymous with EKG)
eCRF	Electronic case report form
EDC	Electronic data capture
eGFR	Estimated glomerular filtration rate (Cockroft-Gault formula)
ERER	Event requiring expedited reporting
GFR	Glomerular filtration rate
GGT	Gamma-glutamyl transferase
HMGB1	High mobility group box protein-1
IB	Investigator's brochure
ICF	Informed consent form
ICU	Intensive Care Unit
IL	Interleukin

IRB	Investigation review board
ITT	Intention-to-treat
LDH	Lactate dehydrogenase
LPS	Lipopolysaccharide
mAb	Monoclonal antibody
MERS-CoV	Middle East respiratory syndrome coronavirus
NS	Not stated
PBMC	Peripheral blood mononuclear cell
PEEP	Positive end-expiratory pressure
PHI	Personal health information
PID#	Participant identification designation number
PK	Pharmacokinetic
PM	Particulate matter
PM _{2.5}	Particulate matter of a size < 2.5 μm
PP	Per-protocol
SARS-CoV	Severe acute respiratory syndrome coronavirus
SARS-CoV-2	2 Severe acute respiratory syndrome coronavirus, type 2
SAE	Serious adverse event
SAP	Statistical analysis plan
SOC	Standard of care
SUSAR	Suspected unexpected serious adverse reaction
TBI	Traumatic brain injury

ULN Upper limit of normal


APPENDIX A: Exc	lusionary period for a	nti-cytokine agents	
CATEGORY	Generic name	Brand name	Exclusionary
			period
IL-1 inhibitors	Rilonacept	Arcalyst	35 days
	Canakinumab	Ilaris	30 days
	Anakinra	Kineret	30 days
IL-6 inhibitors	Toclizumab	Actemra	50 days
	SIltuximab	Sylvant	100 days
	Sarilumab	Kevzara	105 days
	Atezolizumab	Tencentriq	135 days
	Clazakizumab		120 days
	Olokizumab		120 days
	Sirukumab		120 days
JAK inhibitors	Ruxolitinib	Jakafi	30 days
	Tofacitinib	Xeljanz	30 days
	Oclacitinib	Apoquel	30 days
	Baricitinib	Olumiant	30 days
	Peficitinib	Smyraf	30 days
	Fedratinib	Inrebic	30 days
	Upadacitinib	Rinvoq	30 days
	Filgotinib		30 days
	Cerdulatinib		30 days
	Gandotinib		30 days
	Lestaurtinib		30 days
	Momelotinib		30 days
	Pacritinib		30 days
	Abrocitinib		30 days
TNFα inhibitors	Infliximab	Remicade	50 days
	Etanercept	Enbrel	30 days
	Adalimumab	Humira	75 days
	Certolizumab	Cimzia	55 days
	Golimumab	Simponi	60 days

13. APPENDICES

Note 1: This appendix may be updated through the clinical trial as new agents are either approved or brought into clinical practice. The time prior to enrollment that each drug is to be excluded is listed, but may be updated if new information is published regarding modifications to drug half-life.

Note 2: The decision to initiate treatment with any of the agents listed below is determined either according to the hospital specific SARS-CoV-2 Treatment Algorithm or per individual physician decision. If any agent is started post-enrollment, use should be documented as a concomitant medication. Other study procedures should continue as per the schedule of events.

GeneOne Life Science, Inc.

PATIENT STATE	DESCRIPTOR	SCORE 0
Uninfected	No clinical or virologic evidence of infection	
Ambulatory	Infected, with no limitation of activities	1
	Infected, with limitation of activities	2
Hospitalized	No oxygen therapy	3
Mild disease	Oxygen by mask or nasal canula	4
Hospitalized	Non-invasive ventilation or high-flow oxygen	5
Severe disease	Intubation with mechanical ventilation	6
	Ventilation plus any of vasopressor Rx, RRT, ECMO	7
Death	Death	8

1. INTRODUCTION

This document outlines the statistical methods to be implemented during the analyses of data collected within the scope of GeneOne Life Science Inc.'s Protocol GLS27-005 [Safety, Tolerability, Efficacy and Dose Response of GLS-1027 in the Prevention of Severe Pneumonitis caused by SARS-CoV-2 Infection]. The purpose of this plan is to provide specific guidelines from which the statistical analyses will proceed. Any deviations from this plan will be documented in the clinical study report (CSR).

The reader is referred to the following complementary documents:

- Protocol GLS27-005, version 5.0, dated 11 Aug 2021
- Case Report Form (CRF), version 1.05, dated 08 Feb 2021
- Data Management Plan, version 1.0, dated 04 Feb 2021

2. STUDY OBJECTIVES

2.1. Primary Objectives

The primary objectives of the study are to evaluate the following:

- Incidence of serious adverse events relative to treatment group
- Incidence of treatment failure within 28 days from enrollment

2.2. Exploratory Objectives

The exploratory objectives are:

- Assess the number of days requiring ICU care relative to treatment group.
- Assess the number of days of NIV, high-flow O2 or mechanical ventilation relative to treatment group.
- Assess incidence of WHO COVID-19 Classification levels relative to baseline serum IL-6 level.
- Assess incidence of WHO COVID-19 Classification levels relative to baseline serum ferritin level.
- Assess incidence of WHO COVID-19 Classification levels relative to baseline CRP
- Assess trough level of GLS-1027 relative to serum creatinine.
- Assess the maximal level of Positive End-Expiratory Pressure (PEEP) for subjects who are intubated relative to treatment group.
- Assess the number of days of PEEP > 5 cm H2O for subjects who are intubated relative to treatment group.
- Assess change in WHO COVID-19 Classification level at Day 28 from enrollment, relative to group.
- Assess SARS-CoV-2 IgM antibody responses relative to treatment group.

3. STUDY DESIGN AND PLAN

This is a Phase II, randomized, double-blind, placebo-controlled study to assess 2 dose levels of GLS-1027 for the prevention of treatment failure among participants admitted to the hospital with PCR confirmed infection with SARS-CoV-2 (WHO classification 3 or 4). Subjects can be enrolled up to 72 hours from the time of hospital admission.

Participants will be randomized to placebo or GLS-1027 at either 120 mg or 360 mg daily in a 1:1:1 ratio as adjunctive to standard of care based on the hospital COVID-19 treatment algorithm and/or local COVID-19 treatment practices. Participants will be administered study drug for a maximum treatment period of 14 days or until discharge or death, whichever comes first. Primary outcome will be assessment at day 28, with follow-up to continue to Day 56 to document AEs and outcome as to discharge, death, or WHO COVID-19 classification level if subject remains hospitalized.

All subjects will be considered to have completed the study except for the following circumstances:

- Withdrawal of consent from study
- Loss to follow-up
- Stopped study treatment for any reason other than discharge, pregnancy, or decreased renal function

Table 1: Schedule of Assessments

Tests and Observations	1	2	3	4	5	6	7	8	9	10	11	12	13	14	15	28	56 ^m
Clinical Evaluations																	
Obtain written Informed Consent	Х																
Confirm Eligibility Criteria	Х																
Demographics	Х																
Medical History	Х																
Concomitant Medications	Х	Х	Х	Х	Х	Х	Х	Х	Х	Х	Х	Х	Х	Х	Х	Х	Х
Review Medical Record	Х	Х	Х	Х	Х	Х	Х	Х	Х	Х	Х	Х	Х	Х	Х	Х	Х
WHO COVID-19 Classification (Appendix B)	Х	Х	Х	Х	Х	Х	Х	Х	Х	Х	Х	Х	Х	Х	Х	Х	Х
Safety Evaluations																	
Record Adverse Events	Х	Х	Х	Х	Х	Х	Х	Х	Х	Х	Х	Х	Х	Х	Х	Х	Х
Record AM Vital Signs a	Х	Х	X	Х	Х	Х	Х	Х	Х	Х	Х	Х	Х	Х	Х		
Record Hematology ^b	Х	Х	Х			Х			Х			Х			Х		
Record Basic Metabolic Panel ^c	Х	Х	Х	Х	Х	Х	Х	Х	Х	Х	Х	Х	Х	Х	Х		
Record liver function studies (LFTs) °	Х					Х			Х			Х			Х		
Record other labs ^d (for days available)	Х	Х	Х	Х	Х	Х	Х	Х	Х	Х	Х	Х	Х	Х	Х		
Record Procalcitonin (baseline value) e	Х																
Record admission CXR	Х																
Record if care given in ICU setting	Х	Х	Х	Х	Х	Х	Х	Х	Х	Х	Х	Х	Х	Х	Х		
Record whether nasal O ₂ prescribed and dose level (L/min) ^f	Х	Х	Х	Х	Х	Х	Х	Х	Х	Х	Х	Х	Х	Х	Х		
Record whether CPAP prescribed and expiratory pressure ⁹	X	X	X	X	Х	Х	X	Х	Х	X	Х	Х	X	Х	X		
Record if mechanically ventilated and level of PEEP, % FiO ₂ h	X	X	Х	X	X	X	Х	X	Х	X	X	X	Х	X	X		
Record if treated by ECMO	X	Х	X	X	X	X	X	X	X	X	X	X	X	X	Х		
Record admission ECG	Х																
Study Related Procedures																	
Administer assigned study drug ¹	Х	Х	X	Х	X	Х	Х	Х	X	Х	Х	X	Х	Х			
Perform urine pregnancy test	Х																
Perform ECG (12-lead) J		Х					Х										
Collect serum for CPK, GGT k	Х						Х										
Collect blood for plasma for PK assessment ¹		Х															
Collect blood for plasma for trough drug measurement (AM blood draw)		Х	Х	Х			Х										
Collect blood for serum (10mL red top,3 tubes)	Х						Х							Х			
Collect blood for PBMCs (10mL ACD; 3 tubes) ⁿ	Х						Х							Х			
Blood volume for serum, PBMCs	60						70							60			_

^a Vital signs to be recorded daily to include: temperature, respiratory rate, heart rate, systolic and diastolic blood pressure

CONFIDENTIAL Page 7 03DEC2021

^b Hematology labs to be recorded (as collected as part of clinical care) and recorded: Hemoglobin, hematocrit, platelets, neutrophils, band forms, lymphocytes, eosinophils

^c Basic metabolic panel labs: Sodium, potassium, creatinine, BUN, glucose, liver function tests; LFTs include AST, ALT, bilirubin (direct), alkaline phosphatase, LDH, albumin.

^d Other labs to be recorded if performed: Ferritin, CRP, IL-6, troponin, D-dimer

^e Procalcitonin: record only initial measurement or within 48 hours of admission and/or SARS-CoV-2 diagnosis (may be performed prior to date of enrollment)

f Record maximal daily level of O2 by nasal cannula prescribed, if participant is receiving O2 by nasal cannula

^g Record maximal daily level of end expiratory pressure delivered by CPAP prescribed, if participant is receiving CPAP

- ⁱ Study drug administration will commence on the day of enrollment if treatment can be administered before 10 pm and then with AM medications thereafter, If, study drug cannot be administered prior to 10 pm on the day of enrollment, then the 1st day of treatment will occur on the day after enrollment.
- ^j Perform a 12-lead ECG on the 2nd day of treatment with study drug between 75 and 90 minutes post-administration on day 2; and on day 15 (± 2 days)
- ^k Serum is collected for CPK and GGT on day 1 and day 7, and weekly thereafter, if values on day 7 are abnormal until return to normal
- ¹ PK assessment will be performed for the initial 15 subjects enrolled. Blood (5 ml) will be collected for plasma collection at baseline (pre-treatment), and then at 1, 2, 4, and 8 hr. Trough measurements will be obtained as indicated for all study participants
- ^m The clinical record should be reviewed at Day 28 and Day 56 as relevant to denote date of discharge, date of death, or clinical status (WHO COVID-19 Classification Level); if discharged, subjects should be contacted by telephone to ascertain clinical status.
- ⁿ PBMCs will be collected at specified sites only

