3. STUDY DESIGN

This is a Phase II, randomized, double-blind, placebo-controlled study to assess 2 dose levels of GLS-1027 for the prevention of treatment failure among participants admitted to hospital with PCR confirmed infection with SARS-CoV-2 (WHO classification 3 or 4). The enrollment period will extend to 72 hours from hospital admission.

Participants will be randomized to placebo or GLS-1027 at either 120 mg or 360 mg daily in a 1:1:1 ratio as adjunctive to standard of care based on the hospital COVID-19 treatment algorithm and/or local COVID-19 treatment practices. Participants will be administered study drug for a maximum treatment period of 28 days or until discharge or death, whichever comes first. Follow-up will continue through to Day 56 to document AEs and outcome as to discharge, death, or WHO COVID-19 classification level if subject remains hospitalized.

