6.1.3 Day 2 through 29 (or until discharge or death)

- Administer study drug with AM medications if calculated creatinine clearance is \geq 60.
- Determine and record WHO COVID-19 classification level (Appendix B)

- Review new concomitant medications
- Record past 24 hour maximal and minimal temperature (°C), respiratory rate, heart rate, systolic and diastolic BP
- Record potential co-morbid complications of SARS-CoV-2 infection to include shortness of breath, arterial thrombosis (myocardial infarction, stroke, peripheral blood clot), mental confusion, death
- Record adverse effects
- Collect and Record labs as indicated in the Schedule of Events: CBC, BMP, LFTs, CRP, ferritin, D-dimer, CPK, IL-6
- Record if care given in ICU setting
- Record ventilatory status: O₂ use, CPAP use, ventilator, ECMO
- Record O₂ flow rate, FiO₂ % (if intubated), CPAP pressure (as relevant), PEEP setting (as relevant)
- Perform ECG (12 lead) on day 2 at 75-90 minutes post dose, and on day 15 ± 2 days
- Collect serum for CPK and GGT (Day 7) and, if abnormal, then weekly until values normalize
- Collect blood for plasma for GLS-1027 trough measurement as indicated in the Schedule of Events
- Collect blood for serum and PBMCs as indicated in the Schedule of Events
- Pharmacy to review patient creatinine and calculated creatinine clearance daily.

6.1.4 Day 56

- Review medical record to document date of discharge or death, as relevant
- Determine and record WHO COVID-19 classification level (Day 56)
- If hospitalized, review chart to document intercurrent AEs
- If not hospitalized, query participant to document intercurrent AE's from the end of the primary study period

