8.4. Analysis of the Exploratory Efficacy Endpoints

PEEP values during intubation will be plotted separately by treatment over time. Assessment of WHO COVID-19 Classification at 28 day relative to treatment group is discussed in Sections 8.1 and 8.2. Shift tables for worst (most extreme) values of serum IL-6 level, serum ferritin level, and CRP relative to baseline will be presented for each WHO COVID-19 Classification level.

The number of days in ICU, requiring mechanical ventilation and of PEEP > 5 cm H₂O will be summarized by treatment using descriptive statistics (sample size, mean, median, SD, minimum, maximum).

The number and percentage of subjects will be summarized by treatment according to their SARS-CoV-2 IgM antibody response. The above exploratory endpoint analyses will be presented for the PP population and individual results will be listed by treatment and study day. No formal statistical analysis is planned.

CONFIDENTIAL Page 12 03DEC2021

The relationship of trough level of GLS-1027 to serum creatinine relative to treatment group will be examined on an adhoc basis and is outside the scope of this document.

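### Protocol and SAP disagree on treatment period (28 v 14 days) and daily recording (to Day 29 v Day 15), and the SAP's ICU and respiratory-support day counts have no stated counting window

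*SAP*

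**What the plan says.** **Treatment period.** Protocol Section 3: "Participants will be administered study drug for a maximum treatment period of 28 days or until discharge or death, whichever comes first". SAP Section 3: "Participants will be administered study drug for a maximum treatment period of 14 days or until discharge or death, whichever comes first".

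**Recording schedule.** Protocol Table S2 marks ICU care, nasal oxygen, CPAP, ventilation with PEEP, and ECMO every day from Day 1 to Day 29. In SAP Table 1 the same rows, among them "Record if care given in ICU setting" and "Record if mechanically ventilated and level of PEEP", are marked from Day 1 to Day 15 and are blank at Days 28 and 56. Footnote m to SAP Table 1 asks for a record review at Days 28 and 56, but names only discharge, death and clinical status by WHO level.

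**Analyses that use these rows.** SAP Section 8.4 summarises "The number of days in ICU, requiring mechanical ventilation" and PEEP above 5 cm H2O. SAP Section 9.7 and Appendix B add days on nasal oxygen, CPAP and ECMO. SAP Section 8.3 sets ICU and ventilation days to zero for a subject who needed neither, and takes primary outcomes to Day 28. No section says over which days the counts run.

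**Version.** SAP Section 1 is written to "Protocol GLS27-005, version 5.0, dated 11 Aug 2021" and to a case report form dated 08 Feb 2021. The version of the supplied protocol cannot be seen.

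**The concern.** Two things are at stake.

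First, the length of the treatment period is part of the definitions, not only of the dosing text. It sets the window in which a hospital transfer or a stopped treatment counts as a primary-endpoint failure, and the window for entry to the per-protocol set. If the documents differ, the same subject can be classified differently.

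Second, a count of days is interpretable only if its window is known and the days inside it are recorded. The SAP takes outcomes to Day 28 but schedules the ICU and respiratory-support entries only to Day 15. A programmer who follows Table 1 would truncate long stays, and could enter zero for a subject whose first ICU or ventilator day came after Day 15. Two arms with different long stays could then look alike.

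**Working it through.** **Step 1: the SAP's own figure.** The dosing row of SAP Table 1 has 14 marks (Days 1 to 14), which agrees with its 14-day text. The protocol's dosing row has Days 1 to 28 and a bracketed Day 29, which agrees with 28 days and a possible Day 2 start. On dosing, each document agrees with itself; the conflict lies between them.

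**Step 2: the texts side by side.**

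| Item | Protocol | SAP |
|---|---|---|
| Treatment period | 28 days (Section 3) | 14 days (Section 3) |
| ICU, oxygen, CPAP, ventilation, ECMO | Days 1–29 (Table S2) | Days 1–15 (Table 1) |
| Transfer counted as failure | within 28 days (8.6) | within 14 days (8.1) |
| Stopping drug counted as failure | before discharge (8.6) | before Day 14 or discharge (8.1) |
| Per-protocol entry without failure | discharge within 28 days (8.1) | discharge within 14 days (6.4) |

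A transfer on Day 20 is a failure under protocol Section 8.6. It falls outside the transfer rule in SAP Section 8.1, although SAP Section 4 lists loss to follow-up with no window. A subject discharged on Day 20 without failure is in the protocol's per-protocol set and outside the SAP's.

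**Step 3: unscheduled days.** To Day 28: 28 − 15 = 13 days, 13/28 = 46%. On the protocol's 29-day schedule: 29 − 15 = 14 days, 14/29 = 48%.

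**Step 4: effect on a count.** For a stay that starts on day *s* (15 or earlier) and lasts *L* days, entries on the SAP schedule = min(*s* + *L* − 1, 15) − *s* + 1. For *s* of 16 or later the result is 0. The stays below are assumptions; the documents give none.

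| Start | Length | Last day | Days on SAP schedule | Days to Day 28 |
|---|---|---|---|---|
| 5 | 11 | 15 | 11 | 11 |
| 5 | 14 | 18 | 11 | 14 |
| 5 | 20 | 24 | 11 | 20 |
| 8 | 10 | 17 | 8 | 10 |
| 8 | 14 | 21 | 8 | 14 |
| 8 | 20 | 27 | 8 | 20 |
| 10 | 19 | 28 | 6 | 19 |
| 16 | 13 | 28 | 0 | 13 |

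A stay that ends by Day 15 loses nothing. With a Day 5 start, 20 v 14 days becomes 11 v 11: a difference of 6 is seen as 0.

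**Step 5: could the SAP recover the missing days?** The discharge date in footnote m is enough for days in hospital. It is not enough for ICU or ventilator days, which need a start and a stop. Listing 16.2.6.4 carries an ICU admission date but no date of leaving the ICU. The per-protocol restriction does not remove the long ventilated stays either: ventilated subjects meet the failure definition and so remain in that set.

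**The case against.** The strongest reply is that there is one coherent design per document and the reader is comparing two versions. The 14-day rule recurs in the SAP's endpoint and per-protocol definitions. The SAP's endpoint also contains high-flow oxygen, non-invasive ventilation and non-study immune modulators, which the supplied protocol's endpoint does not list as failures in that form. This points to a later protocol. It stands as a likely explanation, but it cannot be confirmed here. It also leaves the missing counting window untouched, because that lies within the SAP.

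A second reply is that the Day 15 cut is inferred. No SAP rule truncates the counts, the ventilation, oxygen and CPAP listings are dated and state no last day, and Listing 16.2.5.4 still shows blood draws on Days 16, 23 and 28, so Table 1 is not a reliable limit on the data. This stands, and it is why the counts *may* be truncated rather than *are*.

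A third is that the summaries are descriptive and that never-ventilated subjects count as zero, so an effect on prevention would still show. This also stands. Differences disappear only between stays with the same start that both run past Day 15.

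A reader might go further and infer that dosing days after Day 15 have no scheduled safety data. The documents do not support that. The SAP row "Record Adverse Events" is marked at Days 28 and 56, and CPK and GGT continue weekly if abnormal. Under the SAP's own 14 days, even a Day 2 start ends on Day 15, which is a recorded day. The gap in vital signs and laboratory tests arises only if the protocol's dosing is combined with the SAP's schedule. Nor is ECG coverage lost: the protocol, and footnote j in the SAP, both place the last ECG at Day 15 ± 2. A demand that the safety schedule cover every dosing day would exceed the protocol itself, which in Days 16 to 28 has haematology and chemistry only on Days 21 and 28.

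**Conclusion.** The supplied documents contradict each other on the treatment period (28 v 14 days) and on daily ICU and respiratory recording (29 v 15 days). The contradiction carries into two primary-endpoint rules and the per-protocol set, so it must be reconciled before the final analysis. It may be a version mismatch, and nothing here says which period is right.

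Separately, and whichever protocol version applies, the SAP summarises ICU and respiratory-support days without a counting window while scheduling none of them on 13 of the 28 days. Followed as written, the counts may stop at Day 15 and a later first ICU or ventilator day may be entered as zero. The loss per stay runs from nothing (ended by Day 15) to 13 days (ongoing from Day 15 or earlier, or from Day 16, to Day 28).

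This rests on reading Table 1 as the limit of recording. What was captured after Day 15 depends on a case report form that was not supplied and that predates protocol version 5.0. The affected endpoints are exploratory, with no formal test, so this second part is a clarification of moderate weight. It does not establish a safety gap.

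**What to change.** 1. Reconcile the treatment period and the schedule between the protocol in force and the SAP, and carry the result through the transfer and discontinuation rules, the per-protocol definition, Table 1 and the listings. State in the SAP which protocol version these follow.
2. In SAP Sections 8.3 and 8.4, state that days of ICU care, oxygen, CPAP or non-invasive ventilation, mechanical ventilation, ECMO and PEEP above 5 cm H2O are counted from enrolment to Day 28, and that zero means none in that window.
3. At the Day 28 record review already in Table 1, abstract start and stop dates of ICU care, oxygen, CPAP or non-invasive ventilation, ventilation and ECMO. For PEEP days, state how days after Day 15 are to be obtained. First check whether the current case report form already holds these dates.

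The cost is document alignment and a few extra date fields at an existing review. Sample size and the primary test are unchanged.
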